8.2.3.2 Electrocardiograms (ECGs)

Subject must be in supine position in a rested and calm state for at least 5 minutes before ECG assessment is conducted. If the subject is unable to be in the supine position, the subject should be in most recumbent position as possible. The ECG must include the following measurements: Heart Rate, QRS, QT, QTc, and PR intervals. The PI or designated site physician will review all ECGs. Once signed, the original ECG tracing will be retained with the subject's source documents. At the request of the sponsor, a copy of the original ECG will be made available to Amgen.

8.2.3.3 Vital Status

Vital status must be obtained for all subjects within the limits of local law. This includes subjects who may have discontinued study visits with or without withdrawing consent

and should include interrogation of public databases, if necessary. If deceased, the date and reported cause of death should be obtained.

8.2.3.4 Other Safety

8.2.3.4.1 Echocardiogram (ECHO)/Multigated Acquisition (MUGA) Scan

Echocardiogram (ECHO) or multigated acquisition (MUGA) will be performed to assess cardiac ejection fraction and will occur at time points specified in the Schedule of Activities (Section 1.3). ECHO/MUGA should include an evaluation from left ventricular ejection fraction (LVEF). Additional ECHO/MUGA assessments may be performed as clinically indicated.

For subjects developing COVID19 during screening period following screening ECHO assessments, consider repeating ECHO following resolution.

8.2.3.4.2 Hypersensitivity

Hypersensitivity reactions have been reported in patients treated with tarlatamab including rare severe events. Clinical signs and symptoms of hypersensitivity may include but are not limited to rash and bronchospasm. Monitor patients for signs and symptoms of hypersensitivity during treatment with tarlatamab and manage as clinically indicated. Withhold or consider permanent discontinuation of tarlatamab based on severity.

8.2.4 Adverse Events and Serious Adverse Events

The method of recording, evaluating, and assessing causality of adverse events and serious adverse events and the procedures for completing and transmitting serious adverse event reports are provided in Section 11.4.

8.2.4.1 Time Period and Frequency for Collecting and Reporting Safety Event Information

8.2.4.1.1 Adverse Events

The adverse event grading scale to be used for this study will be the CTCAE and is described in Section 11.4.

The investigator is responsible for ensuring that all adverse events observed by the investigator or reported by the subject that occur after first dose of investigational product through the **safety follow-up visit or 60 days after the last day of the dosing interval of investigational product(s) or noninvestigational product(s)/auxiliary medicinal product(s), whichever is later**, are reported using the Events CRF.

8.2.4.1.2 Serious Adverse Events

The investigator is responsible for ensuring that all serious adverse events observed by the investigator or reported by the subject that occur after signing of the informed consent through **the safety follow-up visit or 60 days after the last day of the dosing interval of investigational product(s) or noninvestigational product(s)/auxiliary medicinal product(s), whichever is later** are reported using the Events CRF.

All serious adverse events will be collected, recorded and reported to the sponsor or designee **immediately and no later than** 24 hours of the investigator's awareness of the event, as indicated in Section 11.4. The investigator will submit any updated serious adverse event data to the sponsor **immediately and no later than** 24 hours of it being available.

Since the criteria of the CTCAE grading scale differs from the regulatory criteria for serious adverse events, if adverse events correspond to grade 4 CTCAE toxicity grading scale criteria (eg, laboratory abnormality reported as grade 4 without manifestation of life-threatening status), it will be left to the investigator's judgment to also report these abnormalities as serious adverse events. For any adverse event that applies to this situation, comprehensive documentation of the event's severity must be recorded in the subject medical records.

8.2.4.1.3 Serious Adverse Events After the Protocol-required Reporting Period

During the long-term follow-up period, if the investigator becomes aware of serious adverse events suspected to be related to investigational product after the protocol-required reporting period (as defined in Section 8.2.4.1.2) is completed, then these serious adverse events will be reported to Amgen **immediately and no later than** 24 hours following the investigator's awareness of the event on the Events CRF.

After end of Study, there is no requirement to actively monitor study subjects after the study has ended with regards to study subjects treated by the investigator. However, if the investigator becomes aware of serious adverse events suspected to be related to investigational product, then these serious adverse events will be reported to Amgen **immediately and no later than** 24 hours following the investigator's awareness of the event.

Serious adverse events reported **after the end** of the **study** will be captured within the safety database as clinical trial cases and handled accordingly based on relationship to investigational product. If further safety related data is needed to fulfill any regulatory

reporting requirements for a reportable event, then additional information may need to be collected from the subject's records after the subjects ends the study.

8.2.4.2 Method of Detecting Adverse Events and Serious Adverse Events

Care will be taken not to introduce bias when detecting adverse events and/or serious adverse events. Open-ended and non-leading verbal questioning of the subject is the preferred method to inquire about adverse event occurrence.

8.2.4.3 Follow-up of Adverse Events and Serious Adverse Events

After the initial adverse event/serious adverse event report, the investigator is required to proactively follow each subject at subsequent visits/contacts. All adverse events and serious adverse events will be followed until resolution, stabilization, until the event is otherwise explained, or the subject is lost to follow-up (as defined in Section 7.3). Further information on follow-up procedures is given in Section 11.4.

All new information for previously reported serious adverse events must be sent to Amgen **immediately and no later than** 24 hours following knowledge of the new information. If specifically requested, the investigator may need to provide additional follow-up information, such as discharge summaries, medical records, or extracts from the medical records. Information provided about the serious adverse event must be consistent with that recorded on the Events CRF.

8.2.4.4 Regulatory Reporting Requirements for Serious Adverse Events

If subject is permanently withdrawn from **investigational product(s), and/or noninvestigational product(s)/auxiliary medicinal product(s)** because of a serious adverse event, this information must be submitted to Amgen.

Prompt notification by the investigator to the sponsor of serious adverse events is essential so that legal obligations and ethical responsibilities towards the safety of subjects and the safety of a study treatment under clinical investigation are met.

The sponsor holding the relevant Investigational New Drug/Clinical Trial Application for either tarlatamab or [REDACTED] has a legal responsibility to notify both the local regulatory authority and other regulatory agencies about the safety of tarlatamab or [REDACTED] under clinical investigation. The sponsor will comply with country-specific regulatory requirements relating to safety reporting to the regulatory authority, **external review body**, and investigators.

Individual safety reports for suspected unexpected serious adverse reactions **will be reported by the sponsor** according to local regulatory requirements (**eg, electronic**

submission to the Eudravigilance database in the EU as per EU Clinical Trial Regulation 536/2014) as well as sponsor policy and forwarded to investigators as necessary.

An investigator who receives an individual safety report describing a serious adverse event or other specific safety information (eg, summary or listing of serious adverse events) from the sponsor will file it along with the IB and will notify the **external review body**, if appropriate according to local requirements.

Amgen will prepare a single Development Safety Update Report (also referred to as Annual Safety Report in the European Union) for the Amgen Investigational Product. To ensure that consolidated safety information for the study is provided, this single Development Safety Update Report will also include appropriate information on any other investigational products used in the clinical study, if applicable.

8.2.4.5 Safety Monitoring Plan

Subject safety will be routinely monitored as defined in Amgen's safety surveillance and signal management processes.

8.2.4.6 Other Safety Findings/Special Situations

All medication errors, misuse or abuse of the investigational product when associated with a serious adverse event must be reported to Amgen or designee immediately and no later than 24 hours of the investigator's awareness by collecting and recording the Other Safety Findings (OSF)/Special Situations (SS) event on the Clinical Trial electronic Serious Adverse Event (eSAE) Contingency Report Form and submitting the form to Amgen Global Patient Safety or designee.

Further details and definitions regarding OSF/SS - medication errors, misuse, or abuse, can be found in Section 11.4.

8.2.4.7 Pregnancy

Details of all pregnancies in female partners of male subjects will be collected after the start of study treatment and until **60** days after last dose of investigational product **and/or noninvestigational product(s)/auxiliary medicinal product(s)**.

If a pregnancy is reported, the investigator is to inform Amgen **immediately and no later than** 24 hours of learning of the pregnancy and is to follow the procedures outlined in Section 11.5. Amgen Global Patient Safety will follow-up with the investigator regarding additional information that may be requested.

Abnormal pregnancy outcomes (eg, spontaneous abortion, fetal death, stillbirth, congenital anomalies, ectopic pregnancy) are considered serious adverse events.

Further details regarding pregnancy are provided in Section 11.5.

8.2.5 Clinical Laboratory Assessments

Refer to Section 11.2 for the list of clinical laboratory tests to be performed and to the Schedule of Activities (Section 1.3) for the timing and frequency.

The investigator is responsible for reviewing laboratory test results and recording any clinically relevant changes occurring during the study in the Events CRF. The investigator must determine whether an abnormal value in an individual study subject represents a clinically significant change from the subject's baseline values. In general, abnormal laboratory findings without clinical significance (based on the investigator's judgment) are not to be recorded as adverse events. However, laboratory value changes that require treatment or adjustment in current therapy are considered adverse events. Where applicable, clinical sequelae (not the laboratory abnormality) are to be recorded as the adverse event.

All protocol-required laboratory assessments, as defined in Section 11.2, must be conducted in accordance with the laboratory manual and the Schedule of Activities (Section 1.3).

8.2.6 Pharmacokinetic Assessments

All subjects enrolled will have PK samples assessed.

Blood samples will be obtained for determination of serum concentrations of tarlatamab at the time points specified in the Schedule of Activities (Section 1.3). Blood must not be drawn from a port catheter during IP infusion and must wait 5 minutes after end of infusion prior to PK sample collection. If a permanent central line with more than one lumen is used, blood draws can be done via the lumen that is not used for drug administration. However, the preference is for PK samples to be drawn peripherally. Instructions for the collection and handling of biological samples will be provided by the sponsor. The actual date and time (24-hour clock time) of each sample will be recorded in the eCRF.

Concentrations of tarlatamab will be measured from collected PK samples on an ongoing cohort-by-cohort basis. Cumulative data from any preliminary PK analyses will be made available at the time of dose level review meetings (DLRMs).

Sample collection, processing, storage, and shipping instructions are provided in a separate laboratory manual.

8.2.7 Pharmacogenetic Assessments

If the subject consents to the optional pharmacogenetic portion of this study, DNA analyses may be performed. [REDACTED]

[REDACTED]

[figure not shown]
The final disposition of samples will be described in Section [11.6](#).

[REDACTED]

[figure not shown]
8.2.9 Biomarkers

Biomarkers are objectively measured and evaluated indicators of normal biologic processes, pathogenic processes, or pharmacologic responses to a therapeutic intervention.

8.2.9.1 Biomarker Assessment During the Study

8.2.9.2 Biomarker Discovery

8.2.9.2.1 Biomarker Development/Future Research

Biomarker Development refers to using samples collected for Biomarker Discovery for future research after the study ends. In oncology, there is particular interest in the molecular changes underlying the oncogenic processes that may identify cancer subtypes, stage of disease, assess the amount of tumor growth, or predict disease progression, metastasis, and responses to investigational product(s) or **noninvestigational product(s)/auxiliary medicinal product(s)**.

If consent is provided by subjects, biomarker discovery samples collected at the time points specified in the Schedule of Activities will be retained for future biomarker development as described in Appendix 6 (Section 11.6). No additional samples will be collected for biomarker development/future research.

Amgen or another third-party manufacturer may attempt to develop test(s) designed to identify subjects most likely to respond positively or negatively to tarlatamab.

9. Statistical Considerations

9.1 Statistical Hypotheses

No statistical hypotheses will be tested.

9.2 Sample Size Determination

The sample size in the dose exploration phase is based on practical consideration and is consistent with conventional oncology studies with the objective to estimate the MTD. With 3 subjects in a dose level, there is a 27% to 70% probability of observing at least 1 DLT if the true DLT rate is 10% to 33% and with 4 subjects in a dose level, there is 34% to 80% probability. With 6 subjects in a dose level, there is a 47% to 91% probability of observing at least 1 DLT if the true DLT rate is 10% to 33% and with 10 subjects in a dose level, there is a 65% to 98% probability.

In the dose expansion phase, a subject number of 40 will provide an 87% probability of observing at least 1 adverse event with 5% incidence rate. With the 40 subjects and 20% overall response rate, the expected 95% CI would be 9% to 36%.

9.3 Analysis Sets, Subgroups, and Covariates

9.3.1 Analysis Sets

The Safety Analysis Set will consist of all subjects who receive at least 1 dose of tarlatamab. The analysis of all safety and efficacy endpoints, unless noted otherwise, will be conducted on the Safety Analysis Set.

For Part 1 of the study, the analysis of DLT will be conducted on the DLT Analysis Set, defined as all subjects that are enrolled and receive at least 1 dose of tarlatamab with an evaluable DLT endpoint. The DLT endpoint is evaluable if either: 1) the subject experiences a DLT, or 2) the subject does not experience a DLT and receives IP treatment as planned in cycle 1 and has been followed for safety events a minimum of 28 days from start of treatment

The Interim Efficacy Analysis Set will contain all subjects in the Safety Analysis Set who have had the opportunity to be followed for at least 9 weeks starting from day 1. Subjects who stopped disease assessments prior to 9 weeks will be included in this analysis set if the data cutoff is at least 9 weeks after their first dose date. Interim efficacy analysis will be performed on this Interim Efficacy Analysis Set.

The PK Analysis Set will contain all subjects who have received at least 1 dose of tarlatamab and have at least 1 PK sample collected. These subjects will be evaluated for PK analysis unless the number of data points required for analysis is not enough, or significant protocol deviations have affected the data, or if key dosing or sampling information is missing.

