Dose exploration will begin with treating 3 to 4 subjects at the Dose Level 1 (dose level 1 is the highest dose deemed safe and tolerable in ongoing phase 1 trial of tarlatamab in subjects with small cell lung cancer [Note: based on emerging safety data from Study 20160323, the starting dose may be lower than the highest dose deemed safe and tolerable]). The study DLT period is 28 days. Once all subjects enrolled at a certain dose level are DLT evaluable, a DLRT will convene. For any dose level, and depending on observed safety data, the following recommendation may occur: 1) dose de-escalation to the next lowest dose level, 2) additional enrollment to the current dose level, 3) dose escalation to the next highest dose level. Dose escalation/de-escalation recommendations will be guided by a modified toxicity probability interval design (mTPI-2) model (Guo et al, 2017) with a target toxicity probability of 0.3 (Table 4-2) and equivalence toxicity interval of (25%, 35%). The operating characteristics in Table 4-3 provide the probability of selecting each dose level and the expected number of treated patients at each dose level for given hypothetical true DLT rates.

Table 4-2. Guideline for Escalation/De-escalation

Number of Evaluable Subjects	Number of DLTs	Decision
3-4	0	E ^c
	1	S
	2	D ^b
	≥ 3	DU
5	0-1	E ^c
	2-3	D ^b
	≥ 4	DU
6	0-1	E ^c
	2	S
	3	D ^b
	≥ 4	DU
7-8	0-1	E ^c
	2	S
	3-4	D ^b
	≥ 5	DU
9	≤ 2	E ^c
	3	S
	4	D ^b

Number of Evaluable Subjects	Number of DLTs	Decision
	≥ 5	DU
10 ^a	≤ 2	E ^c
	3	S
	4-5	D ^b
	≥ 6	DU

DLT = dose-limiting toxicity; D = de-escalate to the next lower dose level (can be re-escalated back based on future data); DU = the current dose is unacceptably toxic and can't be re-escalated; E = escalate to the next higher dose; S = stay at the current dose.

^a As appropriate to better understand safety profile for a dose level, the number of evaluable subjects may be expanded up to 10.

^b De-escalate guideline applies only when enrollment is allowed to a lower dose level.

^c If a higher dose level is not allowed, then the current dose level can be expanded.

Table 4-3. Operating Characteristics for mTPI-2 Model

	Dose 1	Dose 2	Early Stopping Probability
Scenario 1			
DLT probability	30%	44%	
Selection probability	67%	20%	13%
Expected # Patients	9	4	
Scenario 2			
DLT probability	13%	30%	
Selection probability	27%	72%	1%
Expected # Patients	7	9	

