4.2.1 Replacement of Subjects

If a subject stops or delays treatment for more than 72 hours for reasons other than DLT during the DLT evaluation period, a replacement subject may be enrolled and assigned to the same dose level.

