6.2.1.2.1 Dose Limiting Toxicity

Dose-limiting toxicity (DLT) is defined as any qualifying toxicity that is at least possibly related to tarlatamab with an onset within the first 28 days following first dose with either of the following criteria:

- Grade 3 adverse event lasting more than 3 days (with the exception of fatigue and Grade 3 non-febrile neutropenia that improves to \leq Grade 1 within 3 weeks including the use of growth factor support per neutropenia management guidelines [see Section 6.8.6]);
- \geq Grade 4 adverse event regardless of duration (with the exception of grade 4 non-febrile neutropenia lasting less than or equal to 7 days including the use of growth factor support per neutropenia management guidelines [see Section 6.8.6]).

Laboratory parameters of Grade 4, not considered clinically relevant and improved to Grade \leq 2 within 72 hours, will not be considered DLT's.

Asymptomatic grade 4 electrolyte abnormalities that last $<$ 72 hours, are not clinically complicated, and resolve spontaneously or respond to conventional medical interventions will not be considered DLTs.

The following adverse events will NOT be adjudicated as DLT regardless of the grade or duration:

- Lymphopenia
- Fever
- Tumor lysis syndrome (TLS) including associated manifestations attributable to TLS (eg, electrolyte abnormalities, renal dysfunction, hyperuricemia)

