- Grade 3 adverse event lasting more than 3 days (with the exception of fatigue and grade 3 non-febrile neutropenia that improves to ≤ grade 1 within 3 weeks including the use of growth factor support per neutropenia management guidelines [protocol Section 6.8.6]);
- ≥ Grade 4 adverse event regardless of duration (with the exception of grade 4 non-febrile neutropenia lasting less than or equal to 7 days including the use of growth factor support per neutropenia management guidelines [protocol Section 6.8.6]).
- Grade 5 adverse event

Laboratory parameters of Grade 3 or 4 of any duration, not considered clinically relevant, will not be considered DLTs.

Grade 4 electrolyte abnormalities that last < 72 hours, are not clinically complicated, and resolve spontaneously or respond to conventional medical interventions will not be considered DLTs.

Date: 24 March 2023 Page 21 of 53

The following adverse events will NOT be adjudicated as DLT regardless of the grade or duration:

- Lymphopenia
- Fever
- Tumor lysis syndrome (TLS) including associated manifestations attributable to TLS (e.g., electrolyte abnormalities, renal dysfunction, hyperuricemia)

DLT Evaluable

The DLT endpoint is evaluable if either: 1) the subject experiences a DLT, or 2) the subject does not experience a DLT and receives IP as planned in cycle 1 and has been followed for safety events a minimum of 28 days from start of treatment.

Maximum Tolerated Dose (MTD)

The MTD will be selected from all tried dose levels that have not been previously declared to be unsafe with a decision according to the mTPI decision table. The MTD will be estimated using isotonic regression (Ji et al, 2010) and the MTD will be the dose level with the estimated DLT rate closest to 0.30.

Treatment-Emergent Adverse Event (TEAE)

TEAE is defined as adverse events starting on or after first dose of tarlatamab as determined by "Did event start before first dose of investigational product" equal to "No" or missing on the Events CRF, and up to and including 47 days after the last dose of tarlatamab excluding the events reported after End of Study date.

Treatment-related Adverse Event (TRAE)

TRAE is defined as treatment-emergent AE that per investigator review has a reasonable possibility of being caused by **tarlatamab** as indicated on the Events CRF page.

5.3 Secondary Endpoint-related Definitions

Best Overall Response (BOR) per RECIST 1.1

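### A toxicity still open at day 28 can be counted as a non-DLT at the interim dose level review, because evaluability does not wait until the event can be classed

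*Protocol*

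**What the plan says.** **Onset.** Protocol 6.2.1.2.1 defines a DLT as a qualifying toxicity, at least possibly related to tarlatamab, "with an onset within the first 28 days following first dose".

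**Duration.** The same section makes some events depend on what happens after onset:
- A Grade 3 event counts if it lasts more than 3 days, "with the exception of fatigue and Grade 3 non-febrile neutropenia that improves to" Grade 1 or lower within 3 weeks.
- A Grade 4 or higher event counts whatever its duration, "with the exception of grade 4 non-febrile neutropenia lasting less than or equal to 7 days including the use of growth factor support".
- Certain Grade 4 laboratory and electrolyte findings are exempt on a 72-hour criterion.

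**Evaluability.** Protocol 9.3.1 gives two ways to be evaluable. Under condition 1 the subject has had a DLT. Under condition 2 he has not, and he "receives IP treatment as planned in cycle 1 and has been followed for safety events a minimum of 28 days from start of treatment". SAP 5.2 (DLT Evaluable) repeats this: he "receives IP as planned in cycle 1 and has been followed for safety events a minimum of 28 days".

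**Review.** Protocol 4.1 says: "Once all subjects enrolled at a certain dose level are DLT evaluable, a DLRT will convene". Section 6.2.1.1 requires at least 3 evaluable subjects before an escalation recommendation.

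**Replacement.** Protocol 4.2.1 allows a replacement subject "If a subject stops or delays treatment for more than 72 hours for reasons other than DLT during the DLT evaluation period".

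**The concern.** The 28 days are a limit on onset in one section and a sufficient length of follow-up in another. For an event whose status depends on its duration, the two do not fit. A subject with Grade 3 neutropenia that began on day 20 and persists on day 28 has not yet met the DLT definition and has the required follow-up. Followed literally, condition 2 lets him count as evaluable without a DLT. Neither document says that such an event is pending, and neither extends follow-up until it can be classed.

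DLT is a primary endpoint, and its count is what Table 4-2 takes in. With cohorts of 3 to 4, one subject can decide between escalating and staying. Neutropenia is named as an identified risk in Protocol 2.3. In the single-step schedule the target dose level is first given on day 8 and again on day 15, so its toxicity can fall late in the window.

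**Working it through.** **1. The plan's own figures.** Protocol 9.2 gives the chance of at least one DLT, 1 − (1 − p)^n, at p = 10% and 33%:
- n = 3: 1 − 0.90³ = 27.1% and 1 − 0.67³ = 69.9% (stated 27% to 70%)
- n = 4: 34.4% and 79.9% (stated 34% to 80%)
- n = 6: 46.9% and 91.0% (stated 47% to 91%)
- n = 10: 65.1% and 98.2% (stated 65% to 98%)

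Every Table 4-2 decision also reproduces with mTPI-2, using the 25% to 35% equivalence interval, the 95% unsafe rule and a Beta(1,1) prior (my assumption). The table is sound. The question is the count put into it.

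**2. When an event can be classed.** An event with onset on day d has been observed for 29 − d days by the end of day 28. If the criterion needs L days, it is still open when 29 − d ≤ L, that is d ≥ 29 − L. The latest classification day is 28 + L.

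| Event type | L (days) | Onset days still open at day 28, if unresolved | Latest classification day |
|---|---|---|---|
| Grade 3 lasting more than 3 days | 3 | 26 to 28 | 31 |
| Grade 4 non-febrile neutropenia | 7 | 22 to 28 | 35 |
| Grade 3 non-febrile neutropenia | 21 | 8 to 28 | 49 |

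Grade 4 and 5 events without a duration exemption are classed at onset and are not affected.

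**3. Which open events still satisfy condition 2.** Table 6-4 interrupts tarlatamab for Grade 3 or 4 non-febrile neutropenia until it improves to Grade 2 or lower. Neutropenia still at Grade 3 when the day 15 dose is due means that cycle 1 was not given as planned, so condition 2 fails. The main exposure is therefore to onsets from day 15 on: days 15 to 28 for Grade 3 neutropenia, 14 days rather than 21.

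**4. Effect of one open event on Table 4-2** (E escalate, S stay, D de-escalate).

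| Evaluable | Counted as non-DLT | Counted as DLT |
|---|---|---|
| 3 or 4 | 0: E | 1: S |
| 5 | 1: E | 2: D |
| 6, 7 or 8 | 1: E | 2: S |
| 9 or 10 | 2: E | 3: S |

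**5. Illustration.** Let a share f of true DLTs be open at the review and counted as zero. The documents give no f, so these values are assumptions. The counted rate is p(1 − f). At p = 44% (Table 4-3, Scenario 1, Dose 2) and n = 3, the chance of E is (1 − 0.44(1 − f))³.

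| f | Chance of E, n = 3 | Chance of E, n = 6 |
|---|---|---|
| 0 | 0.56³ = 17.6% | 17.6% |
| 10% | 0.604³ = 22.0% | 24.0% |
| 25% | 0.67³ = 30.1% | 35.8% |
| 50% | 0.78³ = 47.5% | 60.6% |

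These are chances at a single review, not operating characteristics of the whole design.

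**6. Frequency.** Protocol 2.2.2.3 reports 3/113 Grade 3 and 5/113 Grade 4 neutropenia at any time on treatment. At those rates, the chance that a cohort contains at least one is:
- Grade 3 or 4: 1 − (105/113)³ = 20% for 3 subjects and 1 − (105/113)⁴ = 25% for 4
- Grade 3 only: 1 − (110/113)³ = 7.8% and 1 − (110/113)⁴ = 10.2%

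**The case against.** The strongest reply is that the documents never say that an open event is a non-DLT. Absence of a DLT and 28 days of follow-up are separate requirements. If the event is unresolved, the first is undetermined rather than met. The 28 days are a minimum, and Section 6.2.1.1 speaks of subjects being deemed evaluable, which leaves room for judgement. That stands: the event can be counted as zero, and a reader who infers that the plan requires this goes too far. But nothing obliges the review to wait.

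There are also safeguards. Section 9.4.1.1 has adverse events and DLTs in all subjects considered in dosing decisions. Section 6.2.1.1 brings in the cumulative adverse event profile, Section 4.1 allows doses to be reconsidered for late-onset events, and Appendix 3 has Grade 3 or higher non-DLT toxicities reviewed. Table 4-2 is a guideline. An open event would therefore be in front of the review team. None of these provisions changes the DLT count or makes the team wait.

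Three stronger inferences fail:
- **A wrong final MTD.** Final DLT rates are estimated after escalation (9.4.2.5), and the final MTD or RP2D estimate uses all exploration and expansion data (4.1). An event later classed as a DLT enters through condition 1.
- **20% to 25% of cohorts affected.** That figure counts neutropenia at any time. It is not limited to cycle 1, to events open at day 28, or to events that prove to be DLTs.
- **DLTs lost through replacement.** Section 4.2.1 allows a replacement but does not remove the replaced subject. If his event becomes a DLT, condition 1 includes him.

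**Conclusion.** The gap is real but limited. Evaluability can be reached at day 28, while some events with onset by then can be classed only by about day 31, 35 or 49. An event still open, mainly one that starts after the day 15 dose, can enter the interim review as a non-DLT. One such event is enough to turn a stay (or, at 5 subjects, a de-escalation) into an escalation.

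The size rests on these points:
- The frequency is unknown. For neutropenia, 20% to 25% of cohorts of 3 to 4 is at most an upper illustration, and it assumes that the earlier any-time rates apply here. No onset or duration data are given for other Grade 3 events.
- The final MTD estimate is protected provided that DLT status is updated when the event is classed.
- The point applies only if Part 1 is run. Section 4.1 allows it to be eliminated, and also to be opened later.

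It should be corrected, because the affected count drives escalation and the correction is small.

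**What to change.** In Protocol 9.3.1 and SAP 5.2, add to condition 2:

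> and any tarlatamab-related event with onset in the first 28 days whose DLT status depends on its duration or time to improvement has been followed until it can be classed under Section 6.2.1.2.1; until then the subject is pending and is not entered in Table 4-2 as a non-DLT.

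Three clarifications go with it:
- Events that are never adjudicated as DLTs (Grade 3 fatigue, lymphopenia, fever, tumor lysis syndrome) do not make a subject pending. They have no classifying duration, so a rule covering every Grade 3 or higher event would hold those subjects needlessly.
- Reconcile the laboratory exemptions so that both documents class an event alike. Protocol 6.2.1.2.1 exempts Grade 4 values judged not clinically relevant if they improve to Grade 2 or lower within 72 hours. SAP 5.2 exempts Grade 3 or 4 values judged not clinically relevant, whatever their duration. The electrolyte exemption is restricted to asymptomatic findings only in the protocol.
- State in 4.2.1 that a replaced subject stays in the DLT Analysis Set if his event is later classed as a DLT.

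Apart from that reconciliation, no DLT criterion changes, and no dose changes. The cost is these short edits and, in cohorts with an open event, a dose level review that waits by at most about 3 weeks (day 49 − day 28 = 21 days).
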